#### 1. PROTOCOL DEVELOPMENT

This protocol has been developed using Standard Operating Procedure TM-010-00 developed by Newcastle Biomedicine Clinical Research Platforms (http://www.ncl.ac.uk/crp/assets/documents/SOP%20TM-010-00%20Protocol%20dev%20(final).pdf), the revised CONSORT statement(1) and the extension of the CONSORT statement to cluster randomised trials(2) and the list of required fields for ISRCTN registration (http://www.controlled-trials.com/isrctn/isrctn\_dataset/). The protocol contains all information required for ISRCTN registration, all background and methodological information required by the CONSORT statement, plus additional information as suggested by the Standard Operating Procedure. When ISRCTN registration fields have character limits, statements meeting these character limits are provided first, followed by more detailed, 'in full' information.

#### 2. SOURCES OF FUNDING

The study is funded in full by the UK National Institute of Health Research (NIHR) Public Health Research Programme. Total funding: £1,407,206.

#### 3. STUDY NUMBERS

- ISRCTN registration number: (pending)
- NIHR project number: 09/3001/17
- Newcastle University MyProjects number: BH090197
- Newcastle University Account number: awaiting assignment following confirmation of ethics approval
- ClinicalTrials.gov identifier: (pending)

#### 4. PUBLIC TITLE

Evaluation of the 'Change4Life' convenience store programme to promote sales and consumption of fruit and vegetables, including a cluster randomised controlled trial

# 5. SCIENTIFIC TITLE (IN PICO FORMAT)

A multi-component evaluation of the 'Change4Life' convenience store programme to promote sales and consumption of fruit and vegetables, including: a cluster randomised controlled trial of the effect of the intervention on change in fresh fruit and vegetable consumption over 12 months among regular users of intervention stores compared to regular users of control stores; an economic evaluation; and a process evaluation

#### 6. ACRONYM

C4L c-F+VE (pronounced C4LC5)

#### 7. STUDY BACKGROUND

#### 7.1. Introduction

Consumption of fresh fruit and vegetables (FFV) is important for health, providing many essential micronutrients, including antioxidant vitamins, and a rich source of dietary fibre.(3) Fruit and vegetable consumption also contributes to the maintenance of healthy body weight.(3) The promotion of FFV consumption is a key government health strategy in the UK, underpinned by the 'five-a-day' message (adults in the UK are recommended to eat five, standard 80g portions, of fruit and vegetables per day, which can include up to one portion of fresh whole fruit juice; www.dh.gov.uk), yet average consumption among adults

remains at only around two to three portions per day.(4) Fruit and vegetable consumption is also known to be strongly socio-economically patterned, with lower consumption among more deprived communities.(4) Recently, governments have begun to focus on structural interventions to promote a healthier diet, including FFV intake, among poorer groups, building on the proposed, but as yet unproven, link between convenient retail access to the components of a healthy diet and consumption thereof. For example, since 2004, backed by the Scottish Executive, the Scottish Grocery Federation Healthy Living Programme has promoted FFV, as well as other 'healthier' products, in convenience stores (c-stores), with the rationale that c-stores are often found in more socio-economically deprived areas, within walking distance of people's homes, where access to a supermarket selling a wide range of products may be limited.(5)

Convenience stores are defined as small scale, local grocery stores selling food and drink for off-premises consumption as their main activity, with less than 3000ft floor area, usually selling a limited range of products (typically around 3000 lines) from at least eight of 15 categories designated by the Institute of Grocery Distribution, and open long hours (more than 9am-5pm) on every day of the week.(6) Convenience stores are the most widely distributed type of food store in the UK, numbering around 50,000 in 2008, and representing approximately 20% of the total UK food and grocery market.(6) Convenience stores represent a complex retailing sector, comprising five main components:

- Co-operative Society (e.g. the Co-operative Group, Mid Counties Co-operative)
- Petrol station forecourts (dealer- and company-owned e.g., BP, Shell, Total)
- Multiples (convenience specialists and supermarket based chains e.g., Mills, Tesco Express)
- Symbol, franchise and fascia groups (e.g. Spar, Premier, Nisa, Londis, Lifestyle, Costcutter)
- Non-affiliated independents

More frequent shopping is a growing consumer trend across the whole population and there have been particular increases in sales of fresh foods (including FFV) and food-to-go (especially sandwiches) in c-stores in recent years.(6) More than half of the adult population uses c-stores at least once a week, both for 'top-up' shopping and non-budget-focused needs (e.g. items purchased at a premium price for convenience and quality).(6) Despite this, both anecdotally and empirically, the c-store sector has a long-standing reputation for poor availability and quality of FFV.(7) This is underpinned by a widespread belief among c-store owners and managers that their customers do not want to buy FFV in their stores and that low turnover leads to significant waste.

In England, the Department of Health (DH), working in partnership with the Association of Convenience Stores (ACS), has recently embarked on an initiative to develop and widely implement a similar intervention, as a part of the wider "Change4Life" (C4L) national health promotion programme (http://www.nhs.uk/change4life/Pages/default.aspx). Building on the methods used and lessons learned in Scotland, the c-store C4L FFV intervention has been developed and piloted in 12 demonstration stores in the North East region since October 2008. As of March 2010, the intervention has been rolled out to around 100 stores in the North East and other regions and plans are under way to roll-out to a number of additional stores in six other English regions in 2010-11. To date, in both Scotland and England, only evaluations of implementation and the commercial viability of the interventions have been conducted. These indicate that the intervention results in increased sales of FFV from participating c-stores.(8) However, this does not necessarily mean that the intervention also leads to increased FFV consumption amongst store users. Increased sales of FFV amongst c-stores may represent a displacement of FFV sales from other outlets, or may be associated with overall increased purchasing alongside increased wastage.

Working in collaboration with DH, we will conduct a rigorous outcome evaluation of the c-store C4L FFV intervention to determine the effect on FFV consumption and other markers of dietary quality at an individual level. This will be accompanied by economic and process evaluations providing in-depth insight into the costs and benefits of the intervention and how and why the intervention is or is not effective. This integrated evaluation will provide key information for the development of future UK government policy and extend the evidence base nationally and internationally on the relationship between food retailing and dietary quality.(9)

#### 8. STUDY OBJECTIVES

The primary objective is to answer the question: does the C4L c-store FFV intervention lead to a statistically significant increase in consumption of FFV over 12 months among regular users of intervention stores, compared to regular users of control stores?

Secondary objectives will be to answer the questions:

- What is the effect of the intervention at 12 months on change in other markers of dietary quality among regular users of intervention stores, compared to regular users of control stores?
- What are the resource consequences of the intervention at 12 months and how do they relate to intervention outcomes?
- What is the effect of the intervention on change in shopping habits at 12 months among regular users of intervention stores, compared to regular users of control stores?
- What is the effect of the intervention at 1 and 12 months on change in sales variety, cost and quality of FFV in intervention stores, compared to control stores?
- What variation is there in implementation of the intervention at 1 and 12 months?
- What is the feasibility, acceptability and unexpected consequences of the intervention at 8-10 months among key stakeholders including consumers, retail sector personnel (store managers and owners, instore Fresh Food Champions (see section 18.1.2), and other staff) and intervention implementation professionals (decision makers from the Department of Health, the Association of Convenience Stores and the symbol groups involved in the intervention)?

#### 9. STUDY DESIGN

9.1. A single-centre, unblinded, cluster randomised, controlled, parallel-group, superiority study conducted in the UK; with linked process and economic evaluations.

This research will comprise three linked components – a cluster randomised controlled trial (RCT), an economic cost-effectiveness evaluation, and a process evaluation. These three elements are described separately throughout.

# 9.1.1. Cluster RCT

Although we will measure the impact of the intervention at the individual level, it cannot be delivered at the individual level. A cluster RCT allows the effect of interventions delivered at a group level (in this case clusters of regular users of study stores) to be studied at the individual level and is, therefore, the design of choice in this instance.(10)(9)(8) The unit of randomisation will be c-stores, but data will be collected and analysed at the individual level. Stores will be randomised to either intervention or control (usual practice). We will be unable to blind stores to group allocation. We will not draw participants' or study staff's attention to group allocation, but we may be unable to prevent them becoming aware of this during the study.

#### 9.1.2. Economic evaluation

We will assess the resource consequences and outcomes of the intervention in order to determine if it is unambiguously efficient (i.e. costs are saved and outcomes improved) or, if not, what costs are faced in the setting up of such a programme. These might involve costs being imposed on some sectors and saved by others, as well as trade-offs between costs and outcomes. Assuming that the convenience stores are driven by the profit motive and will judge the outcomes according to profit levels, we will concentrate our evaluation on the Department of Health (DH) and consumers. From the perspective of DH we will calculate the costs of initiating the intervention and, using data relating to the primary outcome, we will calculate the cost per additional portion of FFV consumed. Using secondary data and expert opinion we will also attempt to relate any changes in FFV consumption to changes in health and attempt to indicate the anticipated effect on health spending patterns. Finally, we will assess the impact on individuals of any additional FFV

consumption by comparing the additional cost of FFV *per se* and also assess any impact on total cost of purchasing FFV from a c-store as opposed to a major high street retailer.

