#### 18. INTERVENTIONS

#### 18.1. Intervention arm

The c-store C4L FFV intervention implemented in development stores involves an in-store 'toolkit', an in-store Fresh Food Champion, and regular support from the DH implementation team. As retailers make a substantial financial contribution to the cost of the intervention, it also involves the presence of a committed retailer. Although the main intervention components are consistent across stores, there will naturally be store-to-store variation in implementation, as expected in a pragmatic trial.

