# 18.1.1. In-store toolkit

The in-store toolkit comprises C4L branded chiller cabinet, impulse stand, ambient shelving, on-street A-stand, and vinyl window display. The total cost of this is in the region of £15-20,000 per store depending on size and any alterations required to accommodate the new materials. DH contributes an average of £3000 per store, and retailers make up the difference.

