#### 23.2. Economic evaluation

The majority of the data used in the economic evaluation will be collected as part of the cluster RCT and process evaluation components and assessment will, therefore, be as per those components. The topic guide for the qualitative element will incorporate topics relevant to the economic evaluation such as time taken up by the initiative and impact on staff. In addition, costs of the intervention associated with DH and individual c-stores will be assessed, including any labour, consumables and any other costs. Where necessary this additional data will be accessed by telephone calls to the store managers and regional managers. Data from the cluster RCT and process evaluation (e.g. food diary data and shopping habits questionnaire, in store observation and contemporary web data) will be used to estimate costs to consumers associated with changing consumption patterns.

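### The DH cost per additional portion counts only the cost of starting the programme, while the 12-month effect it is divided by also depends on continuing DH support

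*Protocol*

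**What the plan says.** Section 9.1.2 assumes that stores are driven by profit and sets the focus accordingly: "we will concentrate our evaluation on the Department of Health (DH) and consumers". One sentence then gives both the cost and the ratio: "From the perspective of DH we will calculate the costs of initiating the intervention" and, with primary-outcome data, "we will calculate the cost per additional portion of FFV consumed". No other cost-effectiveness ratio is named in the protocol.

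The intervention is described more widely than its start-up:

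- Section 18.1 lists an in-store toolkit, "an in-store Fresh Food Champion, and regular support from the DH implementation team".
- Section 18.1.3 gives the symbol groups' regional managers a continuing liaison and support role.
- Section 18.2 denies control stores DH money, and programme-specific support from the DH team or regional managers, throughout the 12-month intervention period.
- Section 18.3 expects DH team support to run at least until 2011.

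On toolkit cost, section 18.1.1 says: "The total cost of this is in the region of £15-20,000 per store", and "DH contributes an average of £3000 per store, and retailers make up the difference".

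The cost data to be collected are also wider. The objective in section 8 asks: "What are the resource consequences of the intervention at 12 months and how do they relate to intervention outcomes". Section 20.2 collects implementation costs at 12 months from intervention stores, regional managers and DH, and summarises costs separately for DH, stores and consumers. Section 23.2 adds that "costs of the intervention associated with DH and individual c-stores will be assessed, including any labour, consumables and any other costs". Section 28.2 undertakes to set out cost and outcome trade-offs between sectors if the intervention is not unambiguously efficient.

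**The concern.** A cost-effectiveness ratio needs a numerator and a denominator that describe the same thing. The denominator here is the extra FFV eaten at 12 months in intervention stores compared with control stores. That contrast is toolkit plus support against neither. The numerator, as worded, is the cost of getting started. Costs that DH bears during the year to sustain the effect would be left out of a ratio that claims DH's own viewpoint.

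The trial's primary result is not affected. What is at stake is the one figure most likely to be lifted from the economic evaluation and compared with other ways of raising intake. If DH's support costs are material, that figure will look better than it should. If it is also quoted without its perspective, it may be taken for the cost of the whole programme, most of whose equipment is paid for by retailers.

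**Working it through.** The protocol states no cost per portion and no total programme cost, so there is no figure of its own to reproduce. The check has two parts.

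**1. Does the numerator match the denominator from DH's perspective?**

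| Item | In the 12-month effect? | In the ratio as worded? |
|---|---|---|
| DH toolkit contribution (18.1.1) | Yes | Yes |
| Other DH set-up cost (not priced) | Yes | Yes, if it counts as initiation |
| DH team support during the year (18.1, 18.3) | Yes; withheld from controls (18.2) | No |

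Per store, let X be DH's other set-up cost, S be DH's support cost over the 12 months, and E be the additional portions.

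- Ratio as worded: (3000 + X)/E
- Ratio matched to the effect: (3000 + X + S)/E
- Matched divided by worded: 1 + S/(3000 + X)

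E cancels, so power, standard deviation and intraclass correlation play no part. The factor exceeds 1 whenever S is above zero, so the direction is fixed. The protocol prices neither X nor S, so the size is not. The values below are assumptions that only show how the factor moves:

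- X = 0: S = £1,000 gives 1 + 1000/3000 = 1.33; S = £3,000 gives 1 + 3000/3000 = 2.00.
- X = £3,000: S = £1,000 gives 1 + 1000/6000 = 1.17; S = £3,000 gives 1 + 3000/6000 = 1.50.

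Nothing in the protocol selects among these.

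**2. What do the toolkit figures show, and what do they not show?**

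Inputs from 18.1.1: total T = £15,000-20,000 per store; DH pays £3,000 on average.

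- DH share: 3000/15000 = 20% to 3000/20000 = 15%.
- Retailer share: 15000 - 3000 = £12,000 to 20000 - 3000 = £17,000.
- All-payer toolkit cost over DH toolkit cost: 15000/3000 = 5.0 to 20000/3000 = 6.7.

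The 5.0-6.7 range would carry over to the ratio only if DH's whole initiation cost were the £3,000 and nothing else were counted. With other DH set-up cost X in both figures, the factor is (T + X)/(3000 + X):

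- X = £1,000: 16000/4000 = 4.0 to 21000/4000 = 5.25.
- X = £3,000: 18000/6000 = 3.0 to 23000/6000 = 3.8.

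Adding uncounted support S to the all-payer side raises it again. With X = £1,000 and S = £3,000 it is 19000/4000 = 4.75 to 24000/4000 = 6.0. At T = £15,000 the factor stays at 5 or more only if 15000 + X + S ≥ 5(3000 + X), that is, S ≥ 4X. The protocol gives no basis for that condition.

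An absolute cost per portion cannot be worked out either, because the number of regular users per store is not stated.

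**The case against.** The best case for the plan is that section 9.1.2 declares its perspective and gives a reason for it. A public-payer viewpoint is legitimate, and leaving retailers' money out of a DH ratio is not an error. Wider costs are not ignored: sections 20.2 and 23.2 collect them, section 20.2 summarises them by payer, and section 28.2 promises to set costs against outcomes across sectors. The exact list of items in a ratio is often left to an analysis plan, and the word for initiation may simply have been used loosely.

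Most of this stands, and it rules out three stronger readings.

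- A reader might infer that the cost per portion is understated at least five-fold. The documents do not support this. The £3,000 is DH's average toolkit contribution, not its whole initiation cost, and a ratio labelled as one payer's is not understated because other payers exist.
- A reader might infer that the section 8 objective on resources goes unanswered. Sections 20.2, 23.2 and 28.2 address it; what is missing is a named ratio that uses those wider costs.
- A reader might infer that the retailers' £12,000-17,000 should simply be added in. That spending is a commercial investment that higher sales may offset. Section 20.2 looks at store revenue, section 28.2 refers to net costs or profits, and section 18.3 says the toolkit stays in place. Charging its gross cost to one year would mislead in the other direction.

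The perspective argument does not cover DH team support. That falls on DH, belongs to the tested contrast, and is excluded by the wording the protocol itself fixes for the ratio.

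**Conclusion.** The point holds in a limited form. Section 9.1.2 ties the only named ratio to DH's start-up cost, while sections 18.1 to 18.3 make continuing DH support part of what produces the 12-month effect. Followed literally, the DH cost per portion omits a cost that DH bears, and is too low by the factor 1 + S/(3000 + X). Since S and X are not priced, no size can be stated. The conclusion assumes only that the ratio uses the cost named in its own sentence and that DH support is not free.

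The 5.0-6.7 figure describes who pays for the toolkit. It explains why the ratio should not be presented as the programme's resource cost, but it is not a lower bound on any error in it. This is a correction to a secondary analysis, made cheap by the data collection already planned.

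**What to change.** In section 9.1.2, replace the start-up wording with *DH set-up costs plus DH support costs over the 12 months*, costing the support actually delivered. State there that the resulting cost per additional portion is a DH-perspective figure and not the total resource cost of the programme.

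As an optional supplement, report an all-payer cost per additional portion covering DH, retailer and regional-manager costs. Show retailer costs both gross and net of any change in store revenue or profit, and state the toolkit life assumed.

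The cost is a change of wording and slightly more analysis. The DH, store and regional-manager costs are already to be collected under sections 20.2 and 23.2. The downside is a less favourable DH figure.

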#### 9.1.3. Process evaluation

The process evaluation will comprise quantitative and qualitative elements. Quantitative measures will establish the impact of the intervention on the food shopping habits of cluster RCT participants; the effect of the intervention on sales, variety, cost and quality of FFV in intervention stores; and any variation in intervention implementation fidelity or standard. The qualitative element will identify and characterise intervention specific, as well as broader contextual, secular factors considered by stakeholders to have a moderating impact on the intervention, as well as psychosocial and environmental variables influencing response to the intervention. Data will be collected using focus groups with study store customers, and individual in-depth interviews with retail sector personnel and intervention implementation professionals. An ecological framework will provide a structured approach to identifying and exploring the multiple pathways from retail change to diet.

An external store mapping process at baseline and follow-up, using Institute of Grocery Distribution post-code referenced data, will ensure large scale change in the regional retail environment is fully audited and retail grocery structure is fully integrated into the analysis of study outcome measures.

# 10. SETTING, LOCATION AND COUNTRIES OF RECRUITMENT

The study will take place entirely in England, UK. The intervention is a community intervention provided to local c-stores. Details of recruitment and data collection are given in sections 21 and 0.

#### 10.1. Cluster RCT

### 10.1.1. Stores

Participation of stores in the cluster RCT, if selected to take part, will be strongly encouraged by the C4L team. Recruitment will be by letter from the research team to store managers followed by telephone calls and in-store visits.

#### 10.1.2. Individuals

Individual participants in the cluster RCT will be recruited in study stores and data collected from them in their homes.

# 10.2. Economic evaluation

Additional data for the economic evaluation not collected during other components of the study will be collected via web-search, library or other desk based research.

